If a subject shows pulmonary-related signs (hypoxia, fever) or symptoms (eg, dyspnea, cough, fever) consistent with possible pulmonary AEs, the subject should be immediately evaluated to rule out pulmonary toxicity, according to the suspected pulmonary toxicity management algorithm ([Appendix 5](#)) and in the nivolumab Investigator Brochure.⁶⁴

Some of the assessments referred to in this section may not be captured as data in the eCRF. They are intended to be used as safety monitoring by the treating physician. Additional testing or assessments may be performed as clinically necessary or where required by institutional or local regulations.

5.3.1 *Imaging Assessment for the Study*

Any incidental findings of potential clinical relevance that are not directly associated with the objectives of the protocol should be evaluated and handled by the study investigator as per standard medical/clinical judgment. Additional details are provided in the study Imaging Manual.

Radiographic tumor assessments for PCNSL or PTL will be performed ([Section 5.1](#)).

5.4 *Efficacy Assessments*

Radiographic images will be collected for BICR.

5.4.1 *Assessment of Overall Tumor Burden and Disease*

Efficacy assessment will be conducted and reported on the eCRF using the appropriate efficacy assessment based on tumor type. Subjects with PCNSL will be evaluated using the modified International PCNSL Collaborative Group (IPCG) Criteria for PCNSL ([Appendix 3](#)), while subjects with PTL will be evaluated using the Lugano 2014 Classification ([Appendix 4](#)).

The primary efficacy endpoint is ORR based on BICR assessment. BICR will also be used for the assessment of the secondary endpoint PFS. Investigator assessments will be also be used for the ORR and DOR secondary endpoints and the PFS exploratory endpoint.

Efficacy assessments will be required as follows ([Section 5.1](#)):

- PCNSL ([Appendix 3](#))
- PTL ([Appendix 4](#))

Baseline Staging

PCNSL

All PCNSL subjects will undergo gadolinium-enhanced MRI of the brain (and of the spine for subjects with spinal symptoms) at the timepoints specified in [Table 5.1-1](#) and [Table 5.1-2](#) for baseline assessment and on study response assessment purposes. Investigators may obtain more frequent follow-up MRI scans as medically indicated. Local radiologic assessment of tumor measurements will be used for clinical management and investigator-assessed clinical endpoints.

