4 ENDPOINTS

4.1 Primary Endpoint(s)

The primary objective will be measured by the primary endpoint of BICR-assessed ORR. It is defined as the number of participants with a best overall response (BOR) of CR, unconfirmed complete response (CRu) or PR, based on the IPCG Criteria for PCNSL and Lugano 2014 response evaluation for PTL, divided by the number of treated participants within each cohort.

The BICR-assessed BOR is defined as the best response designation recorded between the date of first study drug dose and the date of initial objectively documented progression per criteria or the date of subsequent therapy, whichever occurs first. For purposes of analysis, if a participant receives one dose and discontinues the study without assessment or receives subsequent therapy prior to assessment, this participant will be counted in the denominator (as non-responder).

The BICR-assessed objective response will be further characterized by the time to response (TTR) and duration of response (DOR).

TTR is defined as the time from first dosing date to the date of the first response, based on BICR assessment. TTR will be evaluated for responders only.

DOR is defined as the time from first response (CR, CRu or PR) to the date of initial objectively documented progression as determined using the IPCG Criteria for PCNSL and Lugano 2014 response evaluation for PTL, as determined by BICR, or death due to any cause, whichever occurs first. For participants who neither progress nor die, the DOR will be censored on the date of their last tumor assessment. Participants who start subsequent anticancer therapy without a prior reported progression will be censored at the last tumor assessments prior or on the first subsequent anticancer therapy date. The censoring scheme of DOR will be the same as the primary censoring scheme for PFS. This endpoint will only be evaluated in participants with objective response of CR, CRu or PR.

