4.2 Secondary Endpoint(s)

4.2.1 Progression Free Survival Based on BICR Assessment

PFS is defined as the time from first dosing date to the date of the first documented progression using the IPCG Criteria for PCNSL and Lugano 2014 response evaluation for PTL, as determined by BICR, or death due to any cause, whichever occurs first. Participants who die without a reported progression and did not start a subsequent therapy will be considered to have progressed on the date of their death. Participants who did not progress or die will be censored on the date of their last tumor assessment. Participants who did not have any on study assessments and did not die will be censored on the first dosing date. Participants who started any subsequent anti-cancer therapy without a prior reported progression will be censored at the last tumor assessment prior to initiation of the subsequent anti-cancer therapy.

The censoring scheme is summarized in [Table 4.2.1-1](#).

Table 4.2.1-1: Censoring scheme used in primary analysis of PFS

Situation	Date of Progression or Censoring	Outcome
No baseline tumor assessments and no death	First dosing date	Censored
No on-study tumor assessments and no death	First dosing date	Censored
New subsequent anticancer therapy started without a prior reported progression by IPCG/Lugano 2014 criteria	Date of last evaluable tumor assessment prior to or on the date of initiation of the subsequent anti-cancer therapy	Censored
Progression per IPCG / Lugano 2014 criteria documented at a scheduled or unscheduled visit and no subsequent anticancer therapy started before	Date of the first documented tumor progression per IPCG/Lugano 2014 criteria	Progressed

Table 4.2.1-1: Censoring scheme used in primary analysis of PFS

Situation	Date of Progression or Censoring	Outcome
Participant progression free, no death and no subsequent anti-cancer therapy started	Date of last evaluable tumor assessment per IPCG/Lugano 2014 criteria	Censored
Death without prior progression per IPCG/Lugano 2014 criteria and no subsequent anticancer therapy started	Date of death	Progressed

4.2.2 *Objective Response Rate and Duration of Response Based on Investigator Assessment*

Investigator-assessed ORR and DOR are defined similarly as described for ORR and DOR per BICR assessment above, but will be assessed per investigator.

4.2.3 *Overall Survival*

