8 CONVENTIONS

The following conventions may be used for imputing partial dates for analyses requiring dates:

For missing and partial adverse event onset dates, imputation will be performed using the Adverse Event Domain Requirements Specification¹⁰. Missing and partial Non-Study Medication Domain dates will be imputed using the derivation algorithm described in BMS Non-Study Medication Domain Requirements Specification¹¹.

For death dates, the following conventions will be used for imputing partial dates:

If only the day of the month is missing, the 1st of the month will be used to replace the missing day. The imputed date will be compared to the last known alive date and the maximum will be considered as the death date.

- If the month or the year is missing, the death date will be imputed as the last known alive date.
- If the date is completely missing but the reason for death is present the death date will be imputed as the last known alive date.

For date of progression, the following conventions will be used for imputing partial dates:

- If only the day of the month is missing, the 1st of the month will be used to replace the missing day.
- If the day and month are missing or a date is completely missing, it will be considered as missing.
- In case, the date of death is present and complete, the imputed progression date will be compared to the date of death. The minimum of the imputed progression date and date of death will be considered as the date of progression.

For other partial/missing dates, the following conventions will be used:

- If only the day of the month is missing, the 15th of the month will be used to replace the missing day.
- If both the day and the month are missing, “July 1” will be used to replace the missing information.
- If a date is completely missing, it will be considered as missing.

The following conversion factors will be used to convert days to months or years:

$$1 \text{ month} = 30.4375 \text{ days} \text{ and } 1 \text{ year} = 365.25 \text{ days}$$

Duration (e.g. time from first diagnosis of RCC to first dosing date, duration response, and time to response) will be calculated as follows:

$$\text{Duration} = (\text{Last date} - \text{first date} + 1)$$

All statistical analyses will be carried out using SAS (Statistical Analysis System software, SAS Institute, North Carolina, USA) unless otherwise noted.

Safety conventions from Programming may be summarized separately in an appendix.

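### SAP section 8 caps a day-missing progression date at death but sets no floor, so after an unscheduled assessment the imputed date can precede first dose, a non-progression scan or a response

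*SAP*

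**What the plan says.** SAP section 8 (Conventions) handles a partial progression date in two steps. First: "If only the day of the month is missing, the 1st of the month will be used to replace the missing day". Second: "In case, the date of death is present and complete, the imputed progression date will be compared to the date of death", and then "The minimum of the imputed progression date and date of death will be considered as the date of progression". No comparison is made with the first dosing date, the last assessment without progression or the date of response. SAP 4.1, 4.2.1, Table 4.2.1-1 and 7.5 add none.

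The death-date rule in the same section starts from the same first-of-month imputation but has a lower limit: "The imputed date will be compared to the last known alive date and the maximum will be considered as the death date".

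Three other provisions bear on the consequences:

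- **Duration.** Section 8 calculates durations as last date minus first date plus 1, with no minimum. In SAP 4.2.1, "PFS is defined as the time from first dosing date to the date of the first documented progression".
- **Best overall response.** SAP 4.1 takes the "best response designation recorded between the date of first study drug dose and the date of initial objectively documented progression per criteria", or up to subsequent therapy if that is earlier.
- **Unscheduled assessments.** Table 4.2.1-1 counts progression found at scheduled or unscheduled visits. Protocol 5.4.1 says for PCNSL: "Investigators may obtain more frequent follow-up MRI scans as medically indicated". It allows the same for PET-CT in PTL.

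**The concern.** A first-of-month rule moves a date backwards, so the check it needs is a lower one. The stated check is an upper one and can only move the date further back. If the true progression date is on or before death, the 1st of its month is too, so the check does nothing. It acts only when the recorded progression month is later than the month of death.

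Without a floor, the rule can put events in an impossible order: progression before treatment, before a scan that showed no progression, or before the response whose duration is being measured. The plan does not say how to treat the zero or negative times that result. If the imputed date also closes the best-response window, the primary endpoint is touched. An open-label study is better served by settling this in advance than by a choice made once outcomes are known.

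**Working it through.** The plan gives no figure for this rule, so there is none to reproduce. The check applies the rule literally.

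**Inputs.** Imputed date = 1st of the progression month, capped at a complete death date, and Duration = last - first + 1 (SAP 8). PFS runs from first dose (SAP 4.2.1) and DOR from first response (SAP 4.1). Scans are at Week 8 and then every 8 weeks (56 days) or less often (Protocol 5.4.1). Cohorts are 45 PCNSL and 20 PTL (SAP 5). The examples that section 8 lists for its duration formula do not name PFS; I apply it to PFS as well.

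**Progression in the month of first dose.** For a first dose on day d, PFS = 1 - d + 1 = 2 - d days. This is 0 for d = 2, -8 for d = 10 and -18 for d = 20.

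**Worked cases, day of progression missing:**

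| Case | True value | Rule as written | With a floor |
|---|---|---|---|
| A: first dose 10 May, progression 30 May | PFS 21 days | 1 May, PFS -8 | PFS 1 |
| B: first dose 10 May, scan without progression 5 July, progression 28 July | PFS 80 days | 1 July, PFS 53, before the 5 July scan | 6 July, PFS 58 |
| C: response 5 July, progression 28 July | DOR 24 days | 1 July, DOR -3 | 6 July, DOR 2 |

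**When the order can reverse.** Let g be the true gap in days from the earlier event to progression. In a month of L days, the order reverses if the earlier event falls on days 2 to L - g, which is L - g - 1 days when positive. A four-year cycle has 1461 days in 48 months, so for g up to 27 the share of calendar dates affected is (1461 - 48(g + 1))/1461:

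- g = 7: 1077/1461 = 73.7%
- g = 14: 741/1461 = 50.7%
- g = 21: 405/1461 = 27.7%
- g = 28: only 30-day months (16, one day each) and 31-day months (28, two days each) contribute: (16 + 56)/1461 = 4.9%
- g = 30 or more: 0%

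These shares are conditional on the day being missing. The scheduled 56-day interval gives 0%.

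**Best overall response, if the imputed date closes the window.**

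- PTL without CNS involvement: Protocol 5.4.1 requires the confirming brain MRI at 8 weeks only with CNS involvement, though certain other tests that were positive must also be repeated. Where no such repeat applies, a response on 8 May and progression later in May gives an imputed date of 1 May, and the response falls outside the window: 1/20 = 5.0 points.
- PCNSL: confirmation by repeat brain MRI at 8 weeks is required. A partial response on 13 March is confirmed 56 days later, on 8 May. Progression later in May is imputed to 1 May, before the confirming scan: 1/45 = 2.2 points if the confirmation is lost.

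**The case against.** The failure needs two uncommon things together: a progression date without its day, and an unscheduled assessment that puts progression in the same calendar month as the earlier event. BICR works from collected images, and a scan normally carries a full date (an assumption; the imaging charter is not available here). The conventions are worded as ones that may be used, and the Data Presentation Plan or the charter could hold a check. Dating progression early can also be a deliberate conservative choice. All of this stands. It limits how often the problem can arise, but the rule as written still lacks a lower limit.

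Three stronger inferences are tempting, and the documents do not support them:

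- **Any response followed by progression in the same month costs ORR points.** A PCNSL response first seen on 8 May with progression later in May would be unconfirmed under the protocol even with complete dates, and likewise in PTL with CNS involvement. SAP 4.1 does not restate confirmation, but the protocol requires it. In PCNSL only the confirming scan is at risk.
- **The imputed date certainly governs best overall response.** SAP 4.1 refers to documented progression. Nothing says that an imputed date overrides the order in which the readers assessed the scans.
- **Early failures drop out of the PFS analysis.** The plan is silent on non-positive times, so their handling is unknown.

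**Conclusion.** The gap is real and minor. The rule has an upper check where a lower one is needed, and it can produce impossible values of PFS and DOR. An effect on ORR is possible only if the imputed date is used to close the best-response window.

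The 5.0 and 2.2 points are the weight of one participant in each cohort, not an estimate of bias. One participant can matter in PTL: in SAP Table 5-1, going from 35% to 30% moves the lower confidence limit from 15.4% to 11.9%, across the 14% benchmark. That would need an affected case at exactly that count, and nothing in the documents makes it likely. The frequency of partial dates is not stated, and I expect few. No reported result is shown to change.

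**What to change.** Replace the day-missing progression rule in SAP section 8 with text such as:

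> For a progression date lacking only its day, use the latest of (a) the 1st of that month, (b) the first dosing date, and (c) the day after the last evaluable assessment without progression, any response included, that comes before the progression record in assessment sequence. Derive this separately for BICR and for the investigator. Do not use assessments made after initial progression. Where a complete death date exists, take the earlier of the result and the death date.

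The limit to assessments before the progression record is essential. Protocol 4.5.6 allows treatment and scans to continue beyond initial progression. With an unrestricted floor, initial progression in May followed by stable disease in July could be re-dated to July, which would lengthen PFS and let a later response count.

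The cost is a short SAP edit and a small programming change. No new data are needed.

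### Partial start dates for subsequent radiotherapy, surgery or transplant are set to the 15th or July 1 with no check against known dates, which can reverse their order with progression

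*SAP*

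**What the plan says.** SAP 8 handles partial dates by type. Adverse event onset dates go to a separate specification, and so do medications: "Missing and partial Non-Study Medication Domain dates will be imputed using the derivation algorithm described in BMS Non-Study Medication Domain Requirements Specification". Death dates have a floor: "The imputed date will be compared to the last known alive date and the maximum will be considered as the death date". Imputed progression dates are capped at a known date of death. Everything else falls to a residual rule. It treats a record that lacks just its day as follows: "If only the day of the month is missing, the 15th of the month will be used to replace the missing day". For a record that gives nothing but the year, the SAP writes: "If both the day and the month are missing, “July 1” will be used to replace the missing information". No comparison with another date is attached to these last two rules.

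SAP 7.5.2.4 counts surgery, radiotherapy, and autologous and allogeneic transplant among subsequent therapies. They are not medications, and the visible text names no other date rule for them.

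The date of subsequent therapy is used in three places:
- **Best overall response (SAP 4.1).** The window ends at progression "or the date of subsequent therapy, whichever occurs first".
- **PFS (SAP Table 4.2.1-1).** The row "New subsequent anticancer therapy started without a prior reported progression by IPCG/Lugano 2014 criteria" censors at the last evaluable assessment on or before the therapy date. The progression row counts an event only if no such therapy came earlier.
- **DOR (SAP 4.1).** It follows the PFS censoring scheme.

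**The concern.** The order of two dates, new therapy and progression, decides whether a participant has a PFS event. A mid-period value imputed to one of them without looking at the other can reverse that order.

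Suppose progression is seen on MRI on 20 May and radiotherapy is recorded only as May of that year. The rule gives 15 May. Table 4.2.1-1 then finds new therapy with no earlier progression and censors at the last scan up to 15 May. On the 8-weekly PCNSL schedule (protocol 5.4.1) that scan is about 25 March. A documented event becomes a censored time 8 weeks earlier. The step back can be longer: PTL scans are 12-weekly after the first 6 months, and post-treatment scans are 6-monthly (protocol Table 5.1-3).

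The SAP sees the need for such checks, since death and progression dates have them. Partial dates are foreseeable because later therapy is also recorded at 3-monthly survival contacts, which may be telephone calls.

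**Working it through.** **Inputs.** The two rules come from SAP 8; N = 45 and 20 and the 14% reference rate from SAP 5. The documents give neither the frequency of partial dates nor the lag from progression to new therapy. I therefore assume a fixed lag of L days, vary L, and spread events evenly over a 365-day year.

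**Only the day missing, therapy truly after progression.** The order is reversed when progression falls after the 15th and therapy starts in the same month. In a month of m days, that is max(0, m − 15 − L) progression days. With seven months of 31 days, four of 30 and one of 28:
- L = 7: (7×9 + 4×8 + 1×6)/365 = 101/365 = 28%
- L = 14: (7×2 + 4×1 + 0)/365 = 18/365 = 5%
- L = 15: 7/365 = 2%
- L ≥ 16: 0

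**Day and month missing, therapy truly after progression.** Progression must fall after 1 July (day 182) and therapy in the same year, giving 365 − 182 − L = 183 − L days:
- L = 7: 176/365 = 48%
- L = 28: 155/365 = 42%
- L = 56: 127/365 = 35%
- L ≥ 183: 0

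**Opposite error: therapy truly L days before progression but imputed on or after it.** The event is then kept although the table would censor it.
- 15th rule: 15 − L days per month. L = 7: 12×8/365 = 96/365 = 26%.
- July 1 rule: 182 − L days. L = 7: 175/365 = 48%.

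A day-by-day enumeration over 2017-2018 gives the same shares.

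**Size on the primary ORR.** The Clopper-Pearson limits reproduce SAP Table 5-1. One response is 1/45 = 2.2 points in PCNSL and 1/20 = 5 points in PTL. Starting from the smallest counts that the SAP presents as excluding 14%:

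| Responders | PCNSL (N = 45) | PTL (N = 20) |
|---|---|---|
| Planning boundary | 13: 28.9% (16.4-44.3) | 8: 40% (19.1-63.9) |
| One lost | 12: 26.7% (14.6-41.9) | 7: 35% (15.4-59.2) |
| Two lost | 11: 24.4% (12.9-39.5) | 6: 30% (11.9-54.3) |

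One lost response leaves the lower limit above 14% in both cohorts; two do not.

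**The case against.** Several objections have force.

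- **No base rate.** Every share above is conditional on a partial date for a non-drug therapy. Therapy is asked about at both follow-up visits and every 3 months after, which should usually narrow the date. A transplant date should be known, because GVHD checks are timed from the infusion. The number of affected participants could be zero. This stands.
- **Loss of responses.** A reader might infer that both rules threaten the primary ORR. The 15th rule moves a date back by too little: new therapy would have to start within about 15 days of the first response. Protocol 5.4.1 asks for confirmation at 8 weeks in PCNSL and in PTL with CNS involvement. The risk is mainly that of a year-only record.
- **Direction.** A reader might infer that PFS and DOR are biased upward. The opposite error is of similar size at the same lag, and the documents do not show which order will be commoner.
- **Therapy before the last dose.** A reader might call such an imputed date impossible. SAP 7.2.2 provides for concurrent surgery, radiotherapy or transplant on study as a relevant deviation, so it can be real.
- **Unseen sources.** SAP 8 says its conventions may be used, and a specification that was not supplied might cover procedures. The SAP names none, and permissive wording leaves the choice open without supplying a safe rule.

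None of this removes the gap. Followed as written, the rule can turn a documented progression into a censored time.

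**Conclusion.** The point holds as a defect in a stated rule whose effect on the results is possible but unquantified. For records with only the day missing, reversal needs therapy within about 15 days after progression, which is plausible for radiotherapy given promptly at progression. For year-only records the chance stays at 35-48% for lags of 7-56 days. Both ranges rest on a fixed lag and events spread evenly over the calendar, and both apply only to partial-date records. PFS and DOR are the endpoints mainly exposed. The documents do not support the stronger claims that events will be lost in number, that PFS or DOR will be inflated on balance, or that the ORR conclusion is at risk from a single case. The correction is worth making because it is cheap and best fixed before results are known in an open-label trial.

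**What to change.** Add one rule to SAP 8 for dates collected as subsequent anti-cancer therapy and not covered by the medication specification. Keep the 15th or July 1 as the starting value, then take the latest of:

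1. that value;
2. the day after the last nivolumab dose;
3. the day after any documented progression or, if there is none, the day after the last tumor assessment showing response, where that progression or assessment lies within the recorded month or year.

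Keep the result inside the recorded month or year and no later than death or the last known alive date. State that a same-day progression still counts as the event, for cases where the following day would leave the recorded period. Keep on-study concurrent therapy (SAP 7.2.2) outside the last-dose floor.

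In the May example the rule gives 21 May if the last dose was earlier, and the event of 20 May is kept. If radiotherapy is recorded only as 2017, the last dose was in June, and the only response assessment was on 26 July with no progression, it gives 27 July and the response is kept. A last-dose floor alone would leave 1 July and lose it.

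List every imputed case, and repeat ORR, PFS and DOR with the opposite order (therapy before the progression or response).

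**Cost:** a paragraph, a few lines of code, one listing and one sensitivity analysis, with no new data. **Downside:** when both dates lie in the same recorded period, the true order is unknown. A therapy that really came first, possibly by months in a year-only record, would be counted as later, and a response to it could be credited to nivolumab. The sensitivity analysis bounds this.
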